1.1. Epidemiology of endometrial cancer

Endometrial cancer is a malignant tumor of the endometrium (distinguished from leiomyosarcoma that forms in the myometrium). Endometrial cancer is **the most common reproductive tumor in women** in developed countries, and its incidence is increasing [1]. The incidence of endometrial cancer has increased in China due to lifestyle changes. In economically developed regions of China, endometrial cancer has surpassed cervical cancer to become the reproductive tract malignant tumor with the highest incidence. According to the latest statistics from the National Cancer Center of China, it is estimated that there are 63400 cases of uterine cancer and 21800 deaths in 2015 in China [2]. The mortality rate of endometrial cancer has also increased. This increase may be due to the proportion of patients with advanced endometrial cancer and high-risk endometrial cancer. The diagnosis and treatment of endometrial cancer have become increasingly important in the field of gynecological oncology.

1.2. Pathological and molecular biology characteristics of endometrial cancer

The pathological subtypes of endometrial cancer include endometrioid carcinoma, clear cell carcinoma, serous carcinoma, and carcinosarcoma. Endometrioid carcinoma is classified as type I endometrial cancer, clear cell carcinoma, serous carcinoma, and carcinosarcoma as type II endometrial cancer based on pathogenesis and molecular characteristics[3]. Type I endometrial cancer has a better outcome and a recurrence rate of 20%, while the recurrence rate of type II endometrial cancer is approximately 50%[4]. A study published in Nature in 2013 analyzed 307 endometrioid carcinomas, 53 endometrial serous carcinomas, and 13 mixed endometrial cancers. The data from that study was obtained from the TCGA database. The study results classified endometrial cancer into 4 subtypes: ultramutated/polymerase ϵ [POLE]-mutated (7%), hypermutated/MSI [MSI-H] (30%), copy number low/microsatellite stable [MSS] (65%), and copy number high/serous like (26%)[5]. Patients with POLE mutations had the best outcome, and most had highly differentiated endometrial cancer. The molecular changes of copy number high/serous-like carcinoma are similar to ovarian serous carcinoma. They had the poorest outcome and were mostly endometrial serous carcinoma and poorly differentiated endometrioid carcinoma. **POLE-mutated and microsatellite unstable types account for approximately 37% of endometrial cancers and have a moderate-high tumor mutation burden. This fact is one of the biological and theoretical bases for immunotherapy of endometrial cancer.**

1.3 Current status of treatment for advanced and recurrent endometrial cancer

Endometrial cancer is limited to the uterus (FIGO stage I-II) in 60%–70% of patients on diagnosis. Local (FIGO stage III) and distal (FIGO stage IV) metastasis comprise 21% and 8% of patients, respectively [6]. The 5-year survival of FIGO stage I–II, FIGO stage III, and

FIGO stage IV are 74%–91%, 57%–66%, and 20%–26%, respectively [6, 7]. Although endometrial cancer has a good prognosis, there is a lack of effective treatments for advanced and recurrent endometrial cancer, and median survival is only 12–15 months [8-10]. The NCCN guidelines recommend using chemotherapy combined with radiotherapy ± surgery as personalized multimodal therapy for advanced endometrial cancer with distal metastases or advanced cancer unsuitable for surgery and chemotherapy-based multimodal therapy for non-pelvic local recurrence. Retrospective studies showed that distal metastasis is an important factor that affects survival in patients with advanced and recurrent endometrial cancer. **Systemic treatment is the cornerstone for treating advanced or recurrent endometrial cancer.** A phase III clinical trial published in the New England Journal of Medicine in 2019 enrolled 736 patients and compared chemoradiotherapy with chemomono-therapy for stage III to IVA endometrial cancer. Patients receiving chemoradiotherapy experienced lower local recurrence, but greater distant metastasis and ultimately progression-free survival (PFS) did not increase [11].

Although systemic chemotherapy is the basis of advanced and recurrent endometrial cancer treatment, **the response of endometrial cancer to chemotherapy is moderate, and there are limited options. Therefore, research on systemic therapeutic regimens for endometrial cancer is key to increasing survival.** NCCN guidelines recommend paclitaxel combined with carboplatin as first-line chemotherapy for advanced/recurrent endometrial cancer. The overall response rate is 40%–62%, and the median survival time is 13–19 months. A phase III clinical trial, GOG209, enrolled 1381 patients with advanced or recurrent endometrial cancer and compared paclitaxel combined with carboplatin (TC regimen) against paclitaxel, doxorubicin, and cisplatin (TAP regimen). The interim analysis showed that there was no statistical difference in PFS (14 vs. 14 months) and OS (32 vs. 38 months) between the TC and the TAP group, but the TC group experienced fewer side effects [8].

Other recommended combination chemotherapy regimens include carboplatin/cisplatin combined with liposomal doxorubicin or doxorubicin. The GOG177 trial compared the combination of cisplatin plus doxorubicin (AP) against cisplatin plus doxorubicin with paclitaxel (TAP) in the treatment of advanced or recurrent endometrial cancer. In the AP group, the objective response rate (ORR) was 34%, and median PFS 12.3 months. In the TAP group, the ORR was 57%, and median PFS 15.3 months. The differences were statistically significant. However, the guideline currently still recommends the AP regimen as the first choice due to toxicity in the TAP group. Other combination therapy regimens include carboplatin/cisplatin combined with docetaxel/ifosfamide, paclitaxel combined with ifosfamide, etc. The efficacy of these combination regimens for advanced/recurrent endometrial cancer ranges from 31% to 81%, but the duration of response is relatively short, and the median survival reported in clinical studies is around one year [12, 13].

Paclitaxel is recommended as the single-agent monochemotherapy of choice in the

treatment of recurrent endometrial cancer. Other options include docetaxel, albumin-bound paclitaxel, doxorubicin, liposomal doxorubicin, topotecan, ifosfamide, carboplatin, and cisplatin. The objective overall response of single-agent monochemotherapy as first-line and second-line chemotherapy for recurrence ranges from 21 to 36% and 4% to 27%, respectively [14, 15].

1.4. The Use of Antiangiogenic Drugs in Advanced/Recurrent Endometrial Cancer

Antiangiogenic drugs exhibit a certain efficacy in the treatment of advanced and recurrent endometrial cancer. Examples include bevacizumab, sunitinib, and lenvatinib single-agent monotherapies, with an efficacy of 12%–15% [16, 17]. A phase II clinical study of bevacizumab for persistent or recurrent endometrial cancer showed a response rate of 13.5% and overall survival (OS) of 10.5 months [18]. A phase II clinical study of oral sunitinib for advanced endometrial cancer in patients who experienced treatment failure with prior chemotherapy reported an ORR of 14% and median PFS of 5.4 months. This result is comparable to the response rate of second-line monochemotherapy in recurrent endometrial cancer (4%–27%) [19]. The NCCN guidelines also recommend bevacizumab plus paclitaxel and carboplatin for advanced and recurrent endometrial cancer.

1.5. Immunotherapy for Endometrial cancer

As mentioned above, **approximately 37% of endometrial cancer cases involve POLE mutation or MSI with a high antigen load resulting from the growing tumor. Up to 80% of endometrial cancer cases show high PD1 or PD-L1 expression;** thus, PD1 or PD-L1 serves as a potential molecular marker for immunotherapy [20]. In a phase II clinical trial (NCT01876511) of pembrolizumab for MMR-deficient solid tumors in patients with at least one chemotherapy failure, 53% (8/15) of endometrial cancer patients achieved an objective response with a disease control rate of 73%; a complete response was seen in 3 patients [21]. In the KEYNOTE-28 trial, 48% of endometrial cancer patients had positive PD-L1 expression during the screening period, and 24 patients were finally enrolled. The ORR of pembrolizumab monotherapy in these patients who failed multiple rounds of chemotherapy was 13% [22]. Compared with the efficacy of second-line single-agent chemotherapy in recurrent endometrial cancer, data from these small-sample size trials were quite satisfactory. **At present, pembrolizumab (anti-PD-1 monoclonal antibody) has obtained FDA approval for MSI or MMR-deficient solid tumors, including endometrial cancer. More** clinical studies have attempted to increase therapeutic efficacy for recurrent endometrial cancer by combining immunotherapy and chemotherapy or other targeted therapies, particularly for patients who lack useful biomarkers. In summary, immunotherapy has become a hot spot in endometrial cancer treatment and offers new hope.

1.6 Background of the investigational drugs

IBI308 is an IgG4 monoclonal antibody that can specifically bind to PD-1 molecules on the surface of lymphocytes, blocking the PD-1/programmed cell death-1 ligand-1 (PD-L1) pathway that results in tumor immune tolerance and reactivating antitumor activity of lymphocytes to achieve tumor treatment. IBI308, nivolumab, and pembrolizumab all have the same target but different amino acid sequences. A phase Ia pharmacokinetics study in patients with advanced solid tumors found that increased *in vivo* exposure to sintilimab is almost proportional to a dose increase in the 1–10 mg/kg range, suggesting linear pharmacokinetics. After a single dose of sintilimab was administered to subjects with solid tumors, the clearance half-life (Geo.Mean [CV%]) was 14.4 [28.9%] days, the clearance rate 11.5[42.5%]mL/h, the steady-state volume distribution 5.43[34.4%]L and the apparent volume distribution 5.77[33.2%]L, with PK characteristics similar to other anti-PD-1 antibodies already on the market (nivolumab and pembrolizumab). The efficacy data of IBI308 come mostly from a phase II key single-arm study (ORIENT-1) of IBI308 monotherapy in the treatment of recurrent or refractory classical Hodgkin lymphoma. Ninety-six patients were enrolled in ORIENT-1, the ORR of the per-protocol set was 65.5%, and the 97% CI was 50.5%–78.6%, which was consistent with the results of the efficacy analysis. Phase III studies on sintilimab have been conducted in several solid tumors, including non-small-cell lung cancer (ORIENT-12).

Anlotinib (AL3818) was approved by the National Medical Products Administration (NMPA, formerly China Food and Drug Administration or CFDA) on May 10th, 2018. Anlotinib is an orally administered tyrosine kinase inhibitor targeting VEGFR, FCFR, EGFR, c-Kit, PDGFR, and c-Met. Preclinical studies show that anlotinib can selectively recognize and bind to VEGFR2 to promote its autophosphorylation and inactivation, inhibiting the proliferation of human umbilical vein endothelial cells and angiogenesis. These results were validated again in the subcutaneous mouse tumor model. A phase I clinical trial on the tolerability and pharmacokinetics (NCT01833923) of anlotinib for advanced solid tumors and a phase II clinical study of anlotinib as a third-line drug for refractory advanced lung cancer (ALTER0302) have been completed. The results show that the side effects of anlotinib are controllable, and anlotinib has broad-spectrum antineoplastic effects on solid tumors. Also, since it is an orally administered drug, anlotinib increases patient compliance. Therefore, investigating the efficacy and safety of anlotinib in the treatment of advanced or recurrent endometrial cancer is of immense significance.

In summary, we will conduct a clinical study to evaluate the efficacy, safety, and tolerability of IBI308 combined with anlotinib for advanced or recurrent endometrial cancer and perform an exploratory analysis on the prognostic factors affecting efficacy.

2. Study Objective

2.1 Primary objective

To assess the objective response rate (ORR) of IBI308 combined with anlotinib for the treatment of recurrent/advanced endometrial cancer based on the irRECIST and RECIST (1.1) criteria.

ORR = complete remission (CR) + partial remission (PR).

2.2 Secondary objectives

- To assess the duration of response (DoR) of IBI308 combined with anlotinib for recurrent/advanced endometrial cancer based on irRECIST and RECIST (1.1) criteria.
- To assess the disease control rate (DCR) of IBI308 combined with anlotinib for recurrent/advanced endometrial cancer based on irRECIST and RECIST (1.1) criteria.
- To assess the time to objective response (TTR) of IBI308 combined with anlotinib for recurrent/advanced endometrial cancer based on irRECIST and RECIST (1.1) criteria.
- To assess the progression-free survival (PFS) of IBI308 combined with anlotinib for recurrent/advanced endometrial cancer based on irRECIST and RECIST (1.1) criteria.
- To assess overall survival (OS) of IBI308 combined with anlotinib for recurrent/advanced endometrial cancer based on irRECIST and RECIST (1.1) criteria.
- To assess the 12-month OS rate of IBI308 combined with anlotinib for recurrent/advanced endometrial cancer based on irRECIST and RECIST (1.1) criteria.
- The incidence of adverse events and serious adverse reactions.

2.3 Exploratory purpose

- To explore the possible effects of PD-L1 expression on efficacy.
- To explore molecular biology markers that can predict efficacy.

3. Study Design

3.1. Overall design

This is a prospective, single-arm, open-label phase II clinical trial in which IBI308 intravenous chemotherapy is combined with oral administration of anlotinib for recurrent or advanced endometrial cancer. The primary objective is to assess the ORR of IBI308 intravenous chemotherapy combined with anlotinib for recurrent or advanced endometrial cancer in patients who failed first-line chemotherapy based on the irRECIST and RECIST 1.1 criteria. Subjects will receive IBI308 200 mg intravenously q3w and anlotinib 12 mg qd d1–

d14 q3w po until a protocol-stipulated treatment termination event occurs. Subject visits will continue after treatment has ended.

Evaluation is performed once after the 2nd treatment cycle (C3) and once after the 4th treatment cycle (C5) since the first dose. Subsequently, an evaluation will be performed once after the 7th treatment cycle (C8) and once after the 10th treatment cycle (C11). After the 10th cycle, an evaluation will be performed once every 4 treatment cycles, and the time window for radiologic evaluation is ± 7 days.

Simon's 2-stage design was used for sample size estimation, with an alpha of 0.05 (one-tailed) and a beta of 0.2 (power of 0.8). Based on existing literature, the ORR of anti-PD-1 monoclonal antibody monotherapy for advanced or recurrent PD-L1-positive endometrial carcinoma in patients who failed first-line chemotherapy is 13%. Assuming that a combination of IBI308 and anlotinib can increase efficacy by 26%, the overall ORR is 39%. The data from at least 23 patients are required to obtain results. Seven patients will be enrolled in stage 1. When the number of valid patients ≤ 1 , combination therapy will be considered not superior to monotherapy, and this trial will be terminated. Otherwise, 16 subjects will be enrolled in stage 2. The trial is rejected if the total number of patients with ORR in the two stages is ≤ 5 .

The intention-to-treat principle will be adopted in the efficacy analysis, and all enrolled subjects will be included. Frequency and percentage will be used for categorical data, and the χ^2 test or exact probability will be used for intergroup comparison. Mean and standard deviation (or median and interquartile range) will be used for quantitative data. The t-test or a non-parametric test will be used for intergroup comparison, the K-M method for survival estimation, and the log-rank test for intergroup comparison.

4. Trial Population

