	
significant clinically rapid progression or patients with an unstable general condition.
 
 3. The cumulative treatment period with anti-PD-1 antibody reaches 2 years; 4. Radiological examination shows that drug discontinuation can be considered for CR subjects who have completed 6 cycles of drug administration. 5. Intolerable toxicity; 6. Poor compliance; 7. Loss to follow-up. 8. The investigator considers that the subject must withdraw from the study.
Treatment regimen	
IBI308: Product name (sintilimab), 200 mg intravenous infusion, qd, d1, q3w,
 
Anlotinib: 12 mg/tablet, one tablet daily, orally half an hour before breakfast, d1–d14, and 1 treatment cycle lasting 3 weeks. The patient will take the study drug until protocol-stipulated treatment withdrawal criteria are fulfilled.

Sample size calculation Statistical methods	
Simon's 2-stage design was used for sample size estimation. An alpha of 0.05 (one-tailed), a beta of 0.2, and a power of 0.8 were used. Based on existing literature, the objective response rate (ORR) of anti-PD-1 monoclonal antibody monotherapy in advanced or PD-L1-positive recurrent endometrial carcinoma after failure of first-line chemotherapy is 13%.
 
Assuming that IBI308 combined with anlotinib can increase efficacy by 26%, the ORR is 39%. At least 23 patients are needed. Seven patients will be enrolled in stage 1. When the number of valid patients < 2, combination therapy is considered not superior to monotherapy, and this trial will be terminated. Otherwise, 16 subjects will be enrolled in stage 2. The trial is rejected if there are ≤5 patients with ORR in the two stages. Percentages, χ^2 test, and analysis of variance are used to analyze efficacy. Descriptive methods and percentages will be used for safety analysis.

Efficacy evaluation	
RECIST (v1.1) and irRECIST criteria are used for radiologic tumor evaluation after the 2nd treatment cycle (\pm 7 days) and after week 4 (\pm 7 days) after the start of dosing. Subsequently, radiologic tumor evaluation will be performed once every 3 treatment cycles (\pm 7 days) until the 10th cycle. After the 10th cycle, radiologic tumor evaluation will be performed every 4

	treatment cycles (\pm 7 days). Additional examinations can be performed if clinical progression occurs.

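### Stopping on 1 or fewer responders among 7 is pre-written as non-superiority to monotherapy, a conclusion that seven patients in a single arm cannot support

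*Protocol*

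**What the plan says.** The sample-size text appears in the Protocol Synopsis and again in section 3.1. It sets a Simon two-stage design with one-sided alpha 0.05 and power 0.8. The null is the response rate of anti-PD-1 monotherapy, which "in patients who failed first-line chemotherapy is 13"%. The target enters only as an assumption: "Assuming that a combination of IBI308 and anlotinib can increase efficacy by 26%, the overall ORR is 39"%.

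"Seven patients will be enrolled in stage 1", and 16 more follow if the trial continues, 23 in total. Section 3.1 stops the trial at 1 or fewer valid patients and the synopsis at fewer than 2. Reading valid patients as responders, these are the same rule. For that stop, section 3.1 fixes the conclusion in advance: "combination therapy will be considered not superior to monotherapy, and this trial will be terminated". The synopsis says the same in nearly the same words.

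If 5 or fewer of 23 respond, the protocol says only that the trial is rejected. It makes no statement about monotherapy there.

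**The concern.** A futility boundary answers one question: is there enough activity to spend more patients under this design? The protocol turns it into a comparative finding against monotherapy, although there is no monotherapy arm and the decision rests on seven patients. The comparator is a fixed historical 13%. Section 1.5 gives the same figure for 24 PD-L1-positive patients on pembrolizumab.

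At stake is what the trial may report after an early stop. A combination that had improved on monotherapy could be recorded as no better than monotherapy because the protocol says so, while the interval planned for the same data would show that the question is open.

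**Working it through.** **Inputs.** From the synopsis and section 3.1: p0 = 0.13, p1 = 0.39, n1 = 7, stop at ≤1, n2 = 16, reject at ≤5 of 23. From section 1.4: "Examples include bevacizumab, sunitinib, and lenvatinib single-agent monotherapies, with an efficacy of 12%–15"%.

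**Step 1. Reproduce the design.**
- Stage-1 stop: P(X1 ≤ 1) = (1−p)^7 + 7p(1−p)^6.
- Success: sum over x1 ≥ 2 of P(X1 = x1) × P(X2 ≥ 6−x1), with X1 ~ Bin(7, p) and X2 ~ Bin(16, p).
- At p = 0.13, success is 0.0456. At p = 0.39, it is 0.8003.
- A search over Simon designs for 13% versus 39% returns 1/7, 5/23 as the optimal design. The protocol's figures are correct.

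**Step 2. What 0 or 1 response in 7 shows (exact 95% Clopper-Pearson).**
- 1/7 = 14.3%. The lower limit is 1 − 0.975^(1/7) = 0.4%. The upper limit solves (1−p)^7 + 7p(1−p)^6 = 0.025, giving 57.9%.
- 0/7 = 0%. The upper limit is 1 − 0.025^(1/7) = 41.0%.
- Both intervals contain 13%, a doubled rate and the 39% target. This step needs no assumption about the true rate.

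**Step 3. How often the label would be applied.** For an illustrative rate about double the null, add the class figure: 13% + 12% = 25% and 13% + 15% = 28%.

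| True ORR | (1−p)^7 | 7p(1−p)^6 | Stage-1 stop, label applied |
|---|---|---|---|
| 13% | 0.377 | 0.395 | 77.2% |
| 25% | 0.133 | 0.311 | 44.5% |
| 28% | 0.100 | 0.273 | 37.3% |
| 39% | 0.031 | 0.141 | 17.2% |

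If the two drugs acted independently, the rate would be 1 − 0.87 × 0.88 = 23.4% to 1 − 0.87 × 0.85 = 26.1%, and the stop probability about 49% to 42%.

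**Step 4. How well the stop separates the two cases.** The stop is 0.772/0.445 = 1.7 to 0.772/0.373 = 2.1 times as likely at 13% as at 25% to 28%. A result of exactly 1/7 is only 0.395/0.311 = 1.3 to 0.395/0.273 = 1.4 times as likely. That can justify not enrolling more patients. It is weak evidence for a statement that the combination adds nothing.

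**The case against.** The strongest reply is that nothing is miscalculated. The rule is calibrated at both 13% and 39%; lower power between them belongs to every two-stage design, and a wide interval to any first stage of seven. Section 11.2 already plans exact Clopper-Pearson intervals for the response rate, so a reader of a stopped trial would see the uncertainty. All of this stands. It does not rescue the sentence, because that interval would contradict the conclusion the protocol prescribes.

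The 25% to 28% can also be challenged. Section 1.4 covers bevacizumab, sunitinib and lenvatinib; the protocol gives no anlotinib response rate in endometrial cancer and nowhere says that the rates add. Other figures in the protocol lead elsewhere. Section 1.5 reports 53% (8/15) for pembrolizumab in MMR-deficient disease, and section 4.1 sets no MMR or PD-L1 requirement. Taking the 30% MSI share from section 1.2 purely as an illustration, 0.30 × 53% + 0.70 × 13% = 25% for anti-PD-1 alone, and adding 12% to 15% gives 37% to 40%. So the 25% to 28% serves only to show scale.

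A reader might infer three stronger points, which the documents do not support:
- *The disputed label falls on half or more of trials at 25% to 28%.* The whole two-stage rule fails in 61% to 50% there, but the label belongs only to the stage-1 stop, at 44% to 37%.
- *The same conclusion is drawn at 5 of 23 or fewer.* The protocol attaches no statement about monotherapy to that outcome.
- *The 39% target, the boundaries or the sample size are wrong.* The target is assumed rather than derived, but the design built on it is correct.

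**Conclusion.** The point holds as one about the conclusion and leaves the design intact. A stop at 1 or fewer of 7 shows insufficient activity to continue under a 13% versus 39% design. It does not establish that the combination fails to improve on monotherapy: the exact intervals reach 57.9% after one response and 41% after none. That result is free of assumptions beyond reading valid patients as responders.

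The frequency depends on the true rate. The label would be applied in 44% to 37% of trials at 25% to 28%, which rests on the additive illustration, and in 17% at the protocol's own target. No decision during the trial changes; what changes is what may be claimed after an early stop.

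**What to change.** In the synopsis and section 3.1, replace the conclusion attached to the stage-1 stop with: *the trial stops for insufficient activity to continue under the 13% versus 39% design; this does not establish that the combination is no better than monotherapy*. Add that the stage-1 response rate will be reported with the exact interval of section 11.2. The text should not instead say that 39% has been shown to be unlikely, since the same intervals include 39%.

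Boundaries, sample size and error rates stay as they are. The cost is one sentence in two places and a less definitive statement after an early stop.
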